### 10.3 Study Hypothesis

We hypothesize:

- Study hypothesis 1: Plasma absorption in participants will be detectable in a percentage of women similar to that seen in HPTN 050 (approximately 33%)
- Study hypothesis 2: Of women with detectable levels of tenofovir, a small fraction will have detectable levels in endometrium, cord blood, placental tissue, and amniotic fluid

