### 10.4 Sample Size

The power of the study can be characterized as follows: if the overall absorption rate (defined as the proportion of women with detectable levels of PMPA in plasma, endometrium, cord blood, placental tissue, and/or amniotic fluid) was expected to be 33%, 16 women would provide 72% power to exclude absorption rate > 60%. In addition, the lower and upper bounds of the exact 95% confidence interval (CI) around the absorption rate are 13% and 57%, respectively, if the observed number of absorption in a cohort of 16 women was 5 (31%: 5 out 16).

For endpoints where no or very low absorption rates are expected (e.g., endometrium, cord blood, placental tissue, and amniotic fluid), 16 women would provide 80% power to exclude absorption rate > 25% assuming the true rate of absorption is 5%. In addition, the upper bounds of the exact 95% confidence interval (CI) around the absorption rate are 20% and 30% if the observed number of absorption in a cohort of 16 women was 0 or 1, respectively.

Additional participants may enroll in the study, at the discretion of the protocol team, to replace currently enrolled participants who receive study gel but whose time of cesarean delivery is greater than 8 hours following the time of study gel administration. Thus, in the event that participants are replaced for this purpose, the total sample size at the end of the study may slightly exceed 16 participants who received study gel.

A sample size of 16 women is insufficient to provide a formal statistical assessment for the comparison between the plasma absorption level observed in HPTN 050 and the one that will be observed in this study.

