### **10.6.2 Primary Analysis**

Descriptive statistics to assess women characteristics will be used: for categorical variables, the number and percent in each category; for continuous variables, the mean, median, standard deviation, quartiles and range (minimum, maximum). Similarly, descriptive statistics for continuous variables will be use to describe levels of tenofovir in levels in plasma, in endometrium, in cord blood, in placental tissue, and in amniotic fluid. If a substantial number of women are below the limit of detection of the assay, descriptive statistics for continuous variables will not be used. Rather, proportion of women with detectable levels will be computed along with an exact 95% confidence interval based on the Clopper-Pearson method.

Blood plasma pharmacokinetics of tenofovir will be evaluated after vaginal administration. Pharmacokinetic parameter estimates will include peak concentration ( $C_{max}$ ), time to peak concentration ( $T_{max}$ ), and area under the concentration time curve (AUC) for tenofovir in the blood. Descriptive statistics will be used to summarize these PK parameters in the cohort. Cord blood, amniotic fluid, placental tissue, and endometrial tissue tenofovir levels will also be summarized using descriptive statistics. The ratio of concentrations of tenofovir in maternal blood relative to temporally matched cord blood, amniotic fluid, and endometrial tissue concentrations, and ratio of maternal blood plasma relative to intracellular peripheral blood mononuclear cell (PBMC) tenofovir and tenofovir diphosphate levels will be calculated and summarized using descriptive statistics.

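### Section 10.4 states 80% power to exclude a tissue, cord blood or amniotic fluid absorption rate above 25%; under the exact 95% interval that the protocol plans, the power is 44%

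*Protocol*

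**What the plan says.** Protocol section 10.4 makes a separate power statement for the endpoints with very low expected absorption, naming cord blood, amniotic fluid, placental tissue and endometrium as examples: "16 women would provide 80% power to exclude absorption rate > 25% assuming the true rate of absorption is 5" (per cent). It then adds that the upper limits of the exact 95% confidence interval "are 20% and 30% if the observed number of absorption in a cohort of 16 women was 0 or 1, respectively". No significance level, sidedness or test is attached to the power figure.

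Section 10.6.2 gives the analysis. If many women fall below the assay's limit, the proportion with detectable levels is reported "along with an exact 95% confidence interval based on the Clopper-Pearson method".

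**The concern.** The two statements in section 10.4 stand next to each other and do not agree. If one detection in 16 leaves an upper limit of 30%, that result cannot count as excluding rates above 25%. By the section's own figures only zero detections would do so, and zero detections in 16 is far from an 80% event at a true rate of 5%.

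This is the only power statement specific to the placental-transfer and endometrial endpoints. It tells a reader that there is about a four-in-five chance of ruling out a rate above 25% for each of them if the true rate is 5%. If the correct chance is below one half, the protocol overstates what 16 women can show.

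**Working it through.** **Inputs.** From section 10.4: n = 16, rate to be excluded 25%, assumed true rate 5%, stated power 80%, printed upper bounds 20% (0 detections) and 30% (1 detection). From section 10.6.2: exact 95% Clopper-Pearson interval. Assumption, because the protocol does not define it: to exclude a rate above 25% means that the upper limit of the planned interval lies below 25%. X is the number of women with a detectable level, binomial with n = 16.

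**1. Reproducing the 80%.** Take the rule that at most one detection counts as success.

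P(X ≤ 1 | 5%) = 0.95^16 + 16 × 0.05 × 0.95^15 = 0.4401 + 0.3706 = 0.8108.

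This matches the stated 80% to within about one percentage point.

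**2. Error of that rule.** At a true rate of exactly 25%:

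P(X ≤ 1 | 25%) = 0.75^16 + 16 × 0.25 × 0.75^15 = 0.0100 + 0.0535 = 0.0635.

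The exact one-sided error is 6.3%, above both 2.5% and 5%.

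**3. Exact upper limits.** For 0/16 the two-sided 95% Clopper-Pearson limit is 1 − 0.025^(1/16). For 1/16 it is the p that solves (1 − p)^16 + 16p(1 − p)^15 = 0.025. The one-sided 95% limits use 0.05 in place of 0.025.

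| Detections | Two-sided 95% upper limit | One-sided 95% upper limit | Printed in 10.4 |
|---|---|---|---|
| 0/16 | 20.6% | 17.1% | 20% |
| 1/16 | 30.2% | 26.4% | 30% |

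In both exact versions, 0/16 lies below 25% and 1/16 lies above it.

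**4. Power under the planned interval.** Only X = 0 succeeds:

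P(X = 0 | 5%) = 0.95^16 = 0.4401, or 44.0%.

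The chance of failing to exclude 25% is 1 − 0.440 = 56.0% for each endpoint. The overstatement is 80 − 44 = 36 percentage points.

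**5. Which other rules would accept 1/16?**

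- One-sided 5% score test: z = (0.0625 − 0.25) / √(0.25 × 0.75 / 16) = −0.1875 / 0.1083 = −1.73, beyond −1.645. It accepts 1/16, so the power is 81.1%.
- One-sided 5% mid-p test: 0.0100 + 0.5 × 0.0535 = 0.037. It also accepts 1/16.
- The same two methods at 2.5% per tail: z = −1.73 does not reach −1.96, and 0.037 exceeds 0.025. Neither accepts 1/16.
- Blaker's exact interval: upper limits 20.1% for 0/16 and 30.0% for 1/16. Again only 0/16 succeeds.

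**6. What 16 women do give at about 80%.** With at most one detection, which has probability 81.1% at a true rate of 5%, the Clopper-Pearson upper limit is at most 30.23%. The study therefore has 81% power to exclude a rate above 30.3%.

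**The case against.** The strongest reply is that section 10.4 never defines exclusion. It gives no error level or test, and the confidence bounds are introduced as an additional description, so the power may rest on another rule. The neighbouring figure of 72% power (33% against 60%) is reproduced by a one-sided 5% normal approximation, which suggests that the power figures were not built on a two-sided exact bound. A one-sided 5% score or mid-p rule does give 81%. This stands to the extent that 44% must be tied to the exact interval. A reader might infer that the power is 44% under any rule, and the documents do not support that. But the protocol names neither approximate rule, and the approximation that reproduces the 72% gives 65.6% here, not 80%. The only interval that the protocol plans for these proportions is exact.

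A second reply is that the link to Clopper-Pearson is loose. Section 10.6.2 uses it only if many women are below the assay limit, and the bounds in 10.4 may come from another exact method. For 5/16 the protocol prints 13% and 57%, where Clopper-Pearson gives 11.0% and 58.7%; Blaker's method gives 13.25% and 56.55%. Both observations are right, but neither changes the result. The condition is likely to be met for endpoints with an expected rate of 5%, and under either method the 1/16 limit is about 30%.

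A third reply concerns weight, and it stands. These are secondary objectives. The analysis is descriptive, and no success criterion or stopping rule is tied to 25%. Section 10.4 characterises the power of 16 women rather than deriving 16 from this target, and the 20% and 30% bounds already show what 0/16 or 1/16 would mean. A reader might infer that the design fails or that the sample must grow, and the documents do not support that.

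A reader might also infer from hypothesis 2 in section 10.3, "Of women with detectable levels of tenofovir, a small fraction will have detectable levels in endometrium" and the other compartments, that the denominator should be only the plasma-positive women, about 5 of 16 at 33%. That does not follow. Section 10.4 computes on all 16, section 10.6.2 reports proportions of women, and no analysis restricted to plasma-positive women is planned. The hypothesis states a scientific expectation and needs no rewording for this point.

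**Conclusion.** The stated 80% is wrong for the analysis that the protocol plans. With 16 women, a true rate of 5% and exclusion judged by the exact 95% interval, the power to exclude a rate above 25% is 44.0%. An exact one-sided 95% bound gives the same 44.0%. The 80% treats one detection in 16 as a success, which the protocol's own 30% bound contradicts.

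The conclusion rests on reading exclusion as the exact upper limit lying below 25%. Only an unstated approximate one-sided 5% rule would support the printed figure. This is a definite error in a stated number, with limited consequence: it misdescribes what the study can show for secondary, descriptive endpoints, but it changes no analysis and no decision.

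**What to change.** In section 10.4, replace the sentence giving 80% power with:

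> Assuming a true rate of 5%, 16 women give 44% power to exclude a rate above 25%, and 81% power to exclude a rate above 30.3% (exact two-sided 95% Clopper-Pearson interval).

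Keep n = 16 and leave hypothesis 2 as it is. Once the method is named here, the bound printed as 20% for 0/16 should be checked against it, since Clopper-Pearson gives 20.6%.

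The cost is one sentence and a less favourable figure. No participants, procedures or analyses change. For scale only: with the same two rates, the smallest sample with at least 80% power under the exact two-sided 95% interval is 27 women (at most 2 detections, power 85.0%). Nothing in the protocol requires that increase.

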HPTN 050 also addressed pharmacokinetics of vaginally administered tenofovir gel. Fourteen of 25 women (56%) with pharmacokinetic results had low, but detectable, serum tenofovir levels (limit of quantitation: 3.0 ng/mL) at some point in the 12 hours after dosing on either Day 0 (following the first dose) or on Day 13 (after daily dosing); three of the 14 had detectable levels on both days. The maximum tenofovir concentrations ( $C_{max}$ ) ranged from 3.0 - 25.8 ng/mL, with no clear dose-concentration relationship identified. For the woman with the 25.8 ng/mL level, this peak level occurred two hours following the dose; the level rapidly declined to 10.9 ng/mL at four hours and was undetectable at 12 hours following the dose. Besides the outlier with the highest tenofovir level, the next highest  $C_{max}$  was 7.1 ng/mL. Considering all women in the PK cohort, the median tenofovir  $C_{max}$  was 3.4 ng/mL (interquartile range: below limit of quantitation [3.0 ng/mL] to 4.7 ng/mL). The median  $C_{max}$  for all subjects (3.4 ng/mL) corresponds to approximately 1% of the maximum ( $C_{max, steady-state (ss)}$ ) and 7% of the minimum (C24 single dose) blood concentrations at steady-state with 300 mg daily oral tenofovir dosing. Findings from CONRAD A04-095 are expected to further inform the pharmacokinetic data on vaginally administered tenofovir gel.

Figure 1 presented below demonstrates tenofovir blood concentration following vaginal administration of tenofovir 1% gel in HPTN 050. All levels for all women with measurable tenofovir levels in the blood are shown. (14 of 25; lower limit of quantitation (LLOQ) approximately 3.0 ng/mL [dotted line]). Legend indicates “cohort” – “ID” – “study day”. For reference the tenofovir level associated with the median 24 hour post-dose blood concentration following an oral 300 mg tenofovir dose is indicated with dashed line.

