**Figure 1 - Tenofovir Blood Concentrations vs. Time after Vaginal Administration**

First letter = Cohort

Cohort A - HIV -uninfected/sexually abstinent

Cohort B - HIV -uninfected/sexually active

Cohort C - HIV-infected/sexually abstinent

Cohort D - HIV-infected/sexually active

4 digits = last 4 digits of participant identifier

Last digit = day of study

The current study will expand the ongoing evaluation of tenofovir gel into the term pregnant population. It is conceivable that the absorption and pharmacokinetics of tenofovir gel in the 3rd trimester of pregnancy may differ from the non-pregnant data above, given increased blood flow to the pelvic tissues and engorgement of the pelvic vessels. With hypothesized increased absorption from the pelvic tissues, the potential for placental transfer exists. This protocol will also evaluate that endpoint.

The validated LCMS (liquid chromatography mass spectrometry) method planned for MTN-002 has a limit of quantitation (LOQ) of 5 ng/mL, but uses only 50 microliters of fluid. Previous methods have had a LOQ of 3 ng/mL but used 250 microliters. Since assay sensitivity is largely determined by mass in the sample, not concentration, this likely represents a 3 fold improvement in sensitivity if we use a similar volume as in previous studies. To improve even further, we are planning to dedicate 1 mL serum for the blood tenofovir assay to further increase the sensitivity, possibly below 1 ng/mL. This may increase the number of samples quantifiable in the blood assuming similar pharmacokinetics as in HPTN 050.

No PK analysis is planned beyond description of  $C_{max}$  and  $T_{max}$ . Estimates of vaginal absorption, systemic clearance, volume of distribution, and half-life require accurate assessment of the initial rise in concentration, area under the concentration time curve (AUC), and terminal elimination slope. Since only the concentration at 1 – 3 time points near  $C_{max}$  in only some women (based on HPTN 050 experience) may be expected to be measurable, data from this study cannot be used to estimate initial absorption, AUC, or terminal elimination slope.

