### 3.2 Secondary Objectives

- Characterize the systemic safety profile of single-dose tenofovir 1% vaginal gel in term gravidas
- Compare 3rd trimester absorption of tenofovir 1% vaginal gel to absorption in non-pregnant recent historic controls
- Assess amniotic fluid, cord blood, endometrial tissue and placental tissue levels following single-dose tenofovir 1% vaginal gel

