## **10.5 Participant Accrual, Follow-up, and Retention**

The accrual period will be 18 months. The study site will recruit and enroll a total of 16 participants. Each participant will be followed for two weeks following gel administration. Once a participant has enrolled in the study, the study site will make every reasonable effort to retain her for the entire study period.

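### Secondary objective 2 compares absorption with HPTN 050, but section 10.4 calls 16 women insufficient without saying for what difference, and section 10.6.2 names no comparison

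*Protocol*

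**What the plan says.** - **Section 3.2** makes it a secondary objective to compare third-trimester "trimester absorption of tenofovir 1% vaginal gel to absorption in non-pregnant recent historic controls", citing the HPTN 050 publication.
- **Section 2.10**, after Figure 1, gives a direction: "With hypothesized increased absorption from the pelvic tissues, the potential for placental transfer exists". It gives no size.
- **Section 10.3** (and 2.11) states hypothesis 1: "Plasma absorption in participants will be detectable in a percentage of women similar to that seen in HPTN 050", put at about 33%. No criterion for similarity is given.
- **Section 10.4** states: "A sample size of 16 women is insufficient to provide a formal statistical assessment for the comparison between the plasma absorption level" in HPTN 050 and in this study. No target difference, SD, alpha, test or power accompanies the sentence.
- **Section 10.6.2** plans descriptive summaries of Cmax, Tmax and AUC in the cohort, and exact intervals for the proportion detectable. It does not mention HPTN 050.
- **Section 2.10** reports HPTN 050: "Fourteen of 25 women (56%) with pharmacokinetic results had low, but detectable, serum tenofovir levels" on Day 0 or Day 13, and "three of the 14 had detectable levels on both days". Median Cmax was 3.4 ng/mL ("interquartile range: below limit of quantitation [3.0 ng/mL] to 4.7 ng/mL"); the highest value was 25.8 and the next 7.1 ng/mL.

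**The concern.** The pregnant versus non-pregnant question appears with two measures (level, percentage detectable) and two expectations (increased, similar). The one sentence on feasibility has no stated basis. An analyst who follows sections 10.4 and 10.6.2 literally has no specified comparison with which to address objective 2.

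The nearest substitute is hypothesis 1, which is weakly informative at n = 16. It also depends on the assay limit. HPTN 050 used a limit of about 3.0 ng/mL, whereas sections 2.10 and 7.9.2 say the MTN-002 assay may read below 1 ng/mL. Without a common limit, the percentage detectable could rise sharply with no change in absorption.

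**Working it through.** **1. The section's own power figure.** The sentence at issue carries no number, but section 10.4 states 72% power to exclude a rate above 60% if the true rate is 33%. One-sample normal approximation, one-sided 5%, n = 16: Φ{[(0.60 − 0.33) − 1.645·√(0.60·0.40/16)] / √(0.33·0.67/16)} = Φ(0.0685/0.1176) = 72.0%. This reproduces. No comparable calculation exists for the HPTN 050 comparison.

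**2. Spread of log Cmax implied by section 2.10.**
- Median and upper quartile: ln(4.7/3.4)/0.6745 = 0.48.
- Second-highest of 25: ln(7.1/3.4)/1.52 = 0.48.
- 56% above 3.0 with median 3.4: ln(3.4/3.0)/0.151 = 0.83.
- Highest of 25: ln(25.8/3.4)/1.96 = 1.03.

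The supported range is therefore 0.48 to about 1.0.

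**3. First-dose reading.** The 14 women were detectable on either of two days, three of them on both. If all 25 were sampled on both days (assumption), that is 17/50 = 34% per day, which matches the protocol's figure of about 33%. If the days are also independent, 1 − 0.66² = 56%, which matches 14/25. The first-dose control median then lies below 3.0 ng/mL. A quarter of two-day maxima exceed 4.7, so per day 1 − √0.75 = 13.4% do. Hence SD = ln(4.7/3.0)/(1.108 − 0.412) = 0.65 and the median is about 2.3 ng/mL.

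**4. Power for Cmax.** Simulated Wilcoxon test, two-sided 5% (assumed), log-normal Cmax, values below 3.0 ng/mL tied, 16 pregnant women. The 12 controls are an assumed lower case.

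| Control distribution | log-SD | Controls | 1.5-fold | 2-fold | 3-fold |
|---|---|---|---|---|---|
| Both days pooled, median 3.4 | 0.48 | 25 / 12 | 67% / 52% | 99% / 93% | 100% / 100% |
| Both days pooled, median 3.4 | 1.0 | 25 / 12 | 21% / 15% | 50% / 36% | 89% / 73% |
| First dose, 34% above 3.0 | 0.65 | 25 / 12 | 40% / 26% | 83% / 67% | >99% / 98% |
| First dose, 34% above 3.0 | 0.83 | 25 / 12 | 26% / 17% | 62% / 46% | 96% / 86% |
| First dose, 34% above 3.0 | 1.0 | 25 / 12 | 19% / 13% | 46% / 32% | 86% / 69% |

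With no true difference, rejection was 4% to 5% throughout. Ignoring censoring, the ratio detectable with 80% power is exp{2.80·SD·√(1/16 + 1/n)}: 1.54 at SD 0.48 with 25 controls. At the other end (first dose, SD 1.0, 12 controls, values tied) a 3.5-fold ratio has 81% power.

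**5. Precision of an estimate.** The 95% CI for the ratio is about ×/÷ exp{1.96·SD·√(1/16 + 1/n)}: 1.35 at SD 0.48 and 1.87 at SD 1.0 with 25 controls, or 2.11 at SD 1.0 with 12. Censoring will widen these.

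**6. Detection rate.** For 16 versus 25 women, power is 34% for 56% versus 80%, 37% for 34% versus 60%, and 86% for 34% versus 80%. Against the fixed 33%, exact 95% intervals for 2 to 9 of 16 all contain 33% (2/16: 1.6% to 38.3%; 9/16: 29.9% to 80.2%). At a true rate of 60%, P(2 ≤ X ≤ 9) = 47%.

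**7. Assay limit.** Under the first-dose distributions above, P(Cmax > 1 ng/mL) = Φ(ln median / SD). This is 90% at SD 0.65, 82% at 0.83 and 75% at 1.0, against 34% above 3.0 ng/mL, with absorption unchanged.

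**The case against.** The case for leaving section 10.4 alone is substantial. The section works in absorption rates, defined as proportions of women detectable. If its absorption level means that, step 6 largely supports the caution. No target difference is named, so the sentence is also true for moderate differences in Cmax: 1.5-fold power is 67% at best in the table. HPTN 050 mixed 0.3% and 1% gel, included HIV-infected women and used another assay. Section 7.3 warns that surgery and anesthesia may transiently lower concentrations. A p-value would mix pregnancy with all of this. All of that stands, and it argues for estimation rather than a required test.

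A reader might infer more than the documents support:
- **That the HPTN 050 figures contradict section 10.4, with 99% power for a doubling.** That power needs log-SD 0.48, the favourable end, and a median pooled over Day 0 and Day 13. On the first-dose reading it is 32% to 83%.
- **That section 2.10 anticipates a doubling.** It gives a direction only.
- **That objective 2 must go unanswered.** Section 10.4 excludes only a formal assessment. The cohort summaries can be set beside HPTN 050, and a method may stand in an analysis plan not shown.

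What the objection does not remove is that the protocol itself fixes the objective, the hypothesis and the feasibility statement, and these do not agree.

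**Conclusion.** The mismatch holds and needs no calculation: a stated comparison, no named analysis, two different expectations, and a feasibility statement without a basis. The size argument holds in part. Insufficient is fair for modest Cmax differences and for most detection-rate differences. It is unsupported as a blanket statement about a large rise in Cmax, for which the ratio detectable with about 80% power runs from roughly 1.5-fold to about 3.5-fold. That range rests on log-normal Cmax, log-SD between 0.48 and about 1.0, 12 to 25 comparable controls (assumed), a two-sided 5% level (assumed) and, for the first-dose rows, sampling of all 25 women on both days.

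The most practical risk is the unmatched assay limit, which alone could move the percentage detectable from about 34% to between 75% and 90%. This is a worthwhile clarification, not a design failure.

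**What to change.** - **Section 10.6.2:** state an estimation comparison, labelled descriptive and non-randomized, of per-woman first-dose Cmax with individual HPTN 050 Day 0 values (1% gel where available). Report the Cmax ratio with 95% CI from a censored log-normal fit, and the difference in percentage above 3.0 ng/mL with 95% CI. Apply the 3.0 ng/mL limit to both studies. Use Day 0 only: a maximum over two days gives controls two chances (56% against 34% in step 3 with no true difference). A Wilcoxon test is optional.
- **Section 10.4:** replace the unqualified statement with the expected precision or the detectable-ratio range, with its SD and number of controls, and say that smaller differences cannot be excluded.
- **Section 10.3 (and 2.11):** reconcile similar with the increase in section 2.10, and tie the percentage to the common 3.0 ng/mL limit.
- **Section 3.2:** name Cmax as the measure compared and call the comparison descriptive.

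The cost is wording and a few lines of analysis code, with no extra participants, samples or visits. It needs the individual HPTN 050 values; Figure 1 is described as plotting those of women with measurable levels. The comparison stays confounded by study, assay, surgery and population.
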